8.1.2 Laboratory test abnormalities

8.1.2.1 Definitions and reporting

Laboratory abnormalities that constitute an Adverse event in their own right (are considered clinically significant, induce clinical signs or symptoms, require concomitant therapy or require changes in study treatment), should be recorded on the Adverse Events eCRF. Whenever possible, a diagnosis, rather than a symptom should be provided (e.g. anemia instead of low hemoglobin). Laboratory abnormalities that meet the criteria for Adverse Events should be followed until they have returned to normal or an adequate explanation of the abnormality is found. When an abnormal laboratory or test result corresponds to a sign/symptom of an already reported adverse event, it is not necessary to separately record the lab/test result as an additional event.

Laboratory abnormalities, that do not meet the definition of an adverse event, should not be reported as adverse events. A Grade 3 or 4 event (severe) as per CTCAE does not automatically indicate a SAE unless it meets the definition of serious as defined below and/or as per investigator's discretion. A dose hold or medication for the lab abnormality may be required by

the protocol in which case the lab abnormality would still, by definition, be an adverse event and must be reported as such.

8.1.3 Adverse events of special interest

Adverse events of special interest (AESI) are defined as events (serious or non-serious) which are ones of scientific and medical concern specific to the sponsor's product or program, for which ongoing monitoring and rapid communication by the investigator to the sponsor may be appropriate. Such events may require further investigation in order to characterize and understand them.

Adverse events of special interest are defined on the basis of an ongoing review of the safety data. AESIs are discussed in detail in the [\[Asciminib Investigator's Brochure\]](#).

8.2 Serious adverse events

8.2.1 Definitions

Serious adverse event (SAE) is defined as one of the following:

- Is fatal or life-threatening
- Results in persistent or significant disability/incapacity
- Constitutes a congenital anomaly/birth defect
- Is medically significant, i.e., defined as an event that jeopardizes the patient or may require medical or surgical intervention to prevent one of the outcomes listed above
- Requires inpatient hospitalization or prolongation of existing hospitalization,
- Note that hospitalizations for the following reasons should not be reported as serious adverse events:
 - Routine treatment or monitoring of the studied indication, not associated with any deterioration in condition
 - Elective or pre-planned treatment for a pre-existing condition that is unrelated to the indication under study and has not worsened since signing the informed consent
 - Social reasons and respite care in the absence of any deterioration in the patient's general condition
- Note that treatment on an emergency outpatient basis that does not result in hospital admission and involves an event not fulfilling any of the definitions of a SAE given above is not a serious adverse event

8.2.2 Reporting

To ensure patient safety, every SAE, regardless of suspected causality, occurring after the patient has provided informed consent and until at least 30 days after the patient has stopped study treatment must be reported to Novartis within 24 hours of learning of its occurrence.

Any additional information for the SAE including complications, progression of the initial SAE, and recurrent episodes must be reported as follow-up to the original episode within 24 hours of the investigator receiving the follow-up information. An SAE occurring at a different time

interval or otherwise considered completely unrelated to a previously reported one should be reported separately as a new event.

Any SAEs experienced after the 30 day safety evaluation follow-up period should only be reported to Novartis if the investigator suspects a causal relationship to the study treatment.

Information about all SAEs is collected and recorded on the Serious Adverse Event Report Form; all applicable sections of the form must be completed in order to provide a clinically thorough report. The investigator must assess and record the relationship of each SAE to each specific study treatment (if there is more than one study treatment), complete the SAE Report Form in English, and submit the completed form within 24 hours to Novartis. Detailed instructions regarding the SAE submission process and requirements for signatures are to be found in the investigator folder provided to each site.

Each re-occurrence, complication, or progression of the original event should be reported as a follow-up to that event regardless of when it occurs. The follow-up information should describe whether the event has resolved or continues, if and how it was treated, whether the blind was broken or not, and whether the patient continued or withdrew from study participation.

If the SAE is not previously documented in the Investigator's Brochure or Package Insert (new occurrence) and is thought to be related to the Novartis study treatment, an oncology Novartis Chief Medical Office and Patient Safety (CMO&PS) department associate may urgently require further information from the investigator for Health Authority reporting. Novartis may need to issue an Investigator Notification (IN), to inform all investigators involved in any study with the same drug that this SAE has been reported. Suspected Unexpected Serious Adverse Reactions (SUSARs) will be collected and reported to the competent authorities and relevant ethics committees in accordance with Directive 2001/20/EC or as per national regulatory requirements in participating countries.

8.3 Emergency unblinding of treatment assignment

Not applicable.

8.4 Pregnancies

To ensure patient safety, each pregnancy occurring while the patient is on study treatment must be reported to Novartis within 24 hours of learning of its occurrence. The pregnancy should be followed up to determine outcome, including spontaneous or voluntary termination, details of the birth, and the presence or absence of any birth defects, congenital abnormalities, or maternal and/or newborn complications.

Pregnancy should be recorded on a Clinical Trial Pregnancy Form and reported by the investigator to the oncology Novartis Chief Medical Office and Patient Safety (CMO&PS). Pregnancy follow-up should be recorded on the same form and should include an assessment of the possible relationship to the study treatment any pregnancy outcome. Any SAE experienced during pregnancy must be reported on the SAE Report Form.

Pregnancy outcome should be collected for the female partners of any male who received asciminib treatment in this study. Consent to report information regarding pregnancy outcome should be obtained from the mother.

For all pregnancies with live birth and/or unknown outcome the newborn has to be followed up to obtain infant health status and development up to twelve months after delivery.

8.5 Warnings and precautions

No evidence available at the time of the approval of this study protocol indicated that special warnings or precautions were appropriate, other than those noted in the provided asciminib Investigator's Brochure or bosutinib label. Additional safety information collected between IB updates will be communicated in the form of Investigator Notifications. This information will be included in the patient informed consent and should be discussed with the patient during the study as needed.

8.6 Data Monitoring Committee

This study will institute a data monitoring committee (DMC) which will function independently of all other individuals associated with the conduct of this clinical trial, including the site investigators participating in the study. The DMC will be constituted prior to the randomization of the first patient. The DMC will be responsible to review safety data at approximately 6 months after the first randomized patient has started study treatment. Subsequent reviews will be conducted approximately every 6 months on an as and when needed basis thereafter (i.e. if significant safety findings are noted). This includes but does not limit the role of the DMC to evaluate these data and to provide recommendations to the sponsor to continue, modify or stop the study early. The DMC will be in place at least until the conduct of the primary analysis.

It is expected that the DMC will consist at a minimum of two physicians with appropriate disease area qualifications and one statistician. There will be a meeting with the DMC describing their roles and responsibilities and discussing potential data format and process issues prior to the finalization of DMC charter.

[figure not shown]
It is envisioned that the DMC may make certain types of recommendations, namely:

- No safety concerns, ethical to continue the study as planned
- Serious safety concerns precluding further study treatment, regardless of efficacy
- Recommendation to continue the study but proposing an amendment to the protocol (e.g., incorporate an additional safety assessments)

8.7 Steering Committee

In order to monitor study conduct, a Steering Committee (SC) will be established comprising investigators participating in the trial. Additionally two sponsor representatives (a physician and a statistician) will be active members of this committee.

The SC will ensure transparent management of the study according to the protocol through recommending and approving modifications as circumstances require. Novartis will make final decisions on trial conduct based on SC recommendations. Together with the clinical trial team, the SC will review protocol amendments as appropriate, and also develop recommendations for publications of study results including authorship rules. The details of the role of the Steering Committee will be defined in a Steering Committee charter.

9 Data collection and management

9.1 Data confidentiality

Information about study subjects will be kept confidential and managed under the applicable laws and regulations. Those regulations require a signed subject authorization informing the subject of the following:

- What protected health information (PHI) will be collected from subjects in this study
- Who will have access to that information and why
- Who will use or disclose that information
- The rights of a research subject to revoke their authorization for use of their PHI.

In the event that a subject revokes authorization to collect or use PHI, the investigator, by regulation, retains the ability to use all information collected prior to the revocation of subject authorization. For subjects that have revoked authorization to collect or use PHI, attempts should be made to obtain permission to collect follow-up safety information (e.g. has the subject experienced any new or worsened AEs) at the end of their scheduled study period.

[figure not shown]
The data collection system for this study uses built-in security features to encrypt all data for transmission in both directions, preventing unauthorized access to confidential participant information. Access to the system will be controlled by a sequence of individually assigned user identification codes and passwords, made available only to authorized personnel who have completed prerequisite training.

Prior to entering key sensitive personally identifiable information (Subject Initials and exact Date of Birth), the system will prompt site to verify that this data is allowed to be collected. If the site indicates that country rules or ethics committee standards do not permit collection of these items, the system will not solicit Subject Initials. Year of birth will be solicited (in the place of exact date of birth) to establish that the subject satisfies protocol age requirements and to enable appropriate age-related normal ranges to be used in assessing laboratory test results.

9.2 Site monitoring

Before study initiation, at a site initiation visit or at an investigator's meeting, Novartis personnel (or designated CRO) will review the protocol and eCRFs with the investigators and their staff. During the study, the field monitor will visit the site regularly to check the completeness of patient records, the accuracy of entries on the eCRFs, the adherence to the protocol to Good Clinical Practice, the progress of enrollment, and to ensure that study treatment is being stored, dispensed, and accounted for according to specifications. Key study personnel must be available to assist the field monitor during these visits.

The investigator must maintain source documents for each patient in the study, consisting of case and visit notes (hospital or clinic medical records) containing demographic and medical information, laboratory data, electrocardiograms, and the results of any other tests or assessments. All information recorded on eCRFs must be traceable to source documents in the patient's file. The investigator must also keep the original signed informed consent form (a signed copy is given to the patient).

The investigator must give the monitor access to all relevant source documents to confirm their consistency with the eCRF entries. Novartis monitoring standards require full verification for the presence of informed consent, adherence to the inclusion/exclusion criteria and documentation of SAEs. Additional checks of the consistency of the source data with the eCRFs are performed according to the study-specific monitoring plan.

9.3 Data collection

For studies using Electronic Data Capture (EDC), the designated investigator staff will enter the data required by the protocol into the Electronic Case Report Forms (eCRF). The eCRFs have been built using fully validated secure web-enabled software that conforms to 21 CFR Part 11 requirements, Investigator site staff will not be given access to the EDC system until they have been trained. Automatic validation programs check for data discrepancies in the eCRFs and, allow modification or verification of the entered data by the investigator staff.

The Principal Investigator is responsible for assuring that the data entered into eCRF is complete, accurate, and that entry and updates are performed in a timely manner.

Data collected by third parties (biochemistry, PCR assessments, biomarkers, PK) will be sent electronically to Novartis.

9.4 Database management and quality control

For studies using eCRFs, Novartis personnel (or designated CRO) will review the data entered by investigational staff for completeness and accuracy. Electronic data queries stating the nature of the problem and requesting clarification will be created for discrepancies and missing values and sent to the investigational site via the EDC system. Designated investigator site staff are required to respond promptly to queries and to make any necessary changes to the data.

Concomitant treatments and prior medications entered into the database will be coded using the WHO Drug Reference List, which employs the Anatomical Therapeutic Chemical classification system. Medical history/current medical conditions and adverse events will be coded using the Medical dictionary for regulatory activities (MedDRA) terminology.

[figure not shown]
Samples and/or data will be processed centrally and the results will be sent electronically to Novartis (or a designated CRO).

Randomization codes and data about all study treatments dispensed to the patient and all IRT assigned dosage changes will be tracked using the Novartis Interactive Response Technology.

For EDC studies, after database lock, the investigator will receive a CD-ROM or paper copies of the patient data for archiving at the investigational site.

10 Statistical methods and data analysis

The data will be analyzed by Novartis and/or designated CRO. It is planned that the data from participating centers in this protocol will be combined, so that an adequate number of patients will be available for analysis.

Study data will be summarized with respect to demographic and baseline characteristics, efficacy observations and measurements, safety observations and measurements, and all relevant PK and PD measurements.

The cut-off date for the primary analysis is defined as the date when all patients have been on study treatment for 24 weeks or discontinued earlier. The cut-off date for the end of study treatment analysis is defined as 30 days after the end of study treatment period (see [Section 4.3](#)) to ensure that all available treatment phase data from all patients up to the last dose of study drug taken in this study, will be analyzed and summarized in the end of study treatment phase CSR. Patients will be further followed for survival and progression for up to 5 years from the date the last randomized patient receives the first study dose. An update analysis of OS and PFS will be performed at the end of the follow-up period in the final study CSR.

10.1 Analysis sets

10.1.1 Full Analysis Set

The **Full Analysis Set (FAS)** comprises all patients to whom study treatment has been assigned by randomization. According to the intention to treat principle, patients will be analyzed according to the treatment and stratum they have been assigned to during the randomization procedure.

10.1.2 Safety set

The **Safety Set** includes all patients who received at least one dose of study treatment. Patients will be analyzed according to the study treatment received, where treatment received is defined as the randomized treatment if the patient took at least one dose of that treatment or the first treatment received if the randomized treatment was never received.

10.1.3 Per-Protocol set

[figure not shown]
The **Per-Protocol Set (PPS)** consists of a subset of the patients in the FAS who are compliant with requirements of the CSP. The PPS will be used for sensitivity analyses on the primary endpoint only.

Oncology standards for protocol deviations potentially leading to exclusion from the PPS are:

- Type of indication different from those required by the CSP
- If prior therapy does not match with CSP requirements in terms of number and types of previous therapy regimens
- Another anti-neoplastic therapy administered after start of study treatment and prior to first efficacy assessment
- Study treatment received different from treatment assigned by randomization

10.1.4 Dose-determining analysis set

Not applicable.

10.1.5 Pharmacokinetic analysis set

The **Pharmacokinetic analysis set (PAS)** includes all patients who provide at least one evaluable PK concentration. For a concentration to be evaluable, patients are required to:

- Take a dose of asciminib prior to sampling,
- Take the same dose of asciminib for at least 3 consecutive days without dose interruption or dose modification prior to sampling,
- For post-dose samples, do not vomit within 4 hours after the dosing of asciminib (this is the current dose); for pre-dose samples do not vomit within 4 hours after the dosing of asciminib prior to sampling (this is the previous dose),
- Have the pre-dose sample collected before the next dose administration.

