Serial PK samples over 12 hours will be collected on Week 2 Day 1 from at least 20 CML-CP patients (full PK group) on the asciminib arm, in addition to trough PK samples. These patients will be identified sequentially at selected sites that are capable of serial PK sampling over 12 hours. In the remaining patients in the asciminib arm and in patients that have switched to asciminib, sparse post-dose PK samples on Week 1 Day 1 and trough PK samples will be collected (sparse PK group).

Figure 4-1 Schematic of Study Design

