 13. Impairment of gastrointestinal (GI) function or GI disease that may significantly alter the absorption of study drug (e.g. ulcerative disease, uncontrolled nausea, vomiting, diarrhea, malabsorption syndrome, small bowel resection, or gastric bypass surgery)
 - 14a. Treatment with medications that meet one of the following criteria and that cannot be discontinued at least one week prior to the start of treatment with study treatment
 - Moderate or strong inducers of CYP3A
 - Moderate or strong inhibitors of CYP3A
 15. Previous treatment with or known/ suspected hypersensitivity to asciminib or any of its excipients.
 16. Previous treatment with or known/ suspected hypersensitivity to bosutinib or any of its excipients.
 17. Participation in a prior investigational study within 30 days prior to randomization or within 5 half-lives of the investigational product, whichever is longer
 18. Pregnant or nursing (lactating) women
 - 19a. Women of child-bearing potential, defined as all women physiologically capable of becoming pregnant, unless they are using highly effective methods of contraception during dosing and for 3 days after last dose of asciminib and one month after last dose of bosutinib. Highly effective contraception methods include:

- Total abstinence (when this is in line with the preferred and usual lifestyle of the subject. Periodic abstinence (e.g., calendar, ovulation, symptothermal, post-ovulation methods) and withdrawal are not acceptable methods of contraception)
- Female sterilization (have had surgical bilateral oophorectomy (with or without hysterectomy) total hysterectomy or bilateral tubal ligation at least six weeks before taking study treatment). In case of oophorectomy alone, only when the reproductive status of the woman has been confirmed by follow up hormone level assessment
- Male sterilization (at least 6 months prior to screening). The vasectomized male partner should be the sole partner for that subject.
- Use of oral, injected or implanted hormonal methods of contraception or placement of an intrauterine device (IUD) or intrauterine system (IUS) or other forms of hormonal contraception that have comparable efficacy (failure rate <1%), for example hormone vaginal ring or transdermal hormone contraception.
- In case of use of oral contraception women should have been stable on the same pill for a minimum of 3 months before taking study treatment.

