10.5.4 Secondary PK objectives

The PK objective is to characterize the PK of asciminib in CML population.

Using PAS, summary statistics (n, mean, SD, coefficient of variation (CV) for mean, geometric mean, CV for geometric mean, median, minimum and maximum) will be presented for plasma concentration at each scheduled time point. The geometric mean with mean (SD) and individual plasma concentration versus time profiles of asciminib will be displayed graphically.

Using Safety set, concentration data will be listed. Concentration values below the limit of quantification (BLQ) will be set to zero by the Bioanalyst and displayed in listings as zero with a flag. BLQ values will be handled as zero in any calculations of summary statistics, but handled as missing for the calculation of the geometric means and CVs.

Pharmacokinetic parameters will be determined by non-compartmental method(s) using the pharmacokinetic profile of asciminib in patients with full PK sampling. PK parameters listed in [Table 10-1](#) will be derived and reported, when feasible.

Population PK modeling may be performed and the results may be reported in a separate population PK report. Data from this study may be combined with data from other studies for this analysis.

Table 10-1 Non compartmental pharmacokinetic parameters in full PK group

AUC0-12h	The area under the plasma concentration-time curve from time zero to 12 h (mass x time x volume-1) ^a
Cmax	The maximum (peak) observed plasma drug concentration after dose administration (mass x volume-1)
Tmax	The time to reach maximum (peak) plasma drug concentration after dose administration (time)
CL/F	The total body clearance of drug from the plasma after oral administration (volume x time-1)

[figure not shown]

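### The three-day dosing condition in section 10.1.5 makes every Week 1 Day 1 asciminib concentration non-evaluable, although section 10.5.4 promises a summary at that time point

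*Combined protocol and SAP*

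**What the plan says.** Section 10.1.5 defines the PAS at patient level. It "includes all patients who provide at least one evaluable PK concentration". Evaluability, however, is defined sample by sample: "For a concentration to be evaluable, patients are required to" meet a list of conditions, the second of which is "Take the same dose of asciminib for at least 3 consecutive days without dose interruption or dose modification prior to sampling". The other conditions are a dose before sampling, no vomiting within 4 hours of the relevant dose, and, for pre-dose samples, collection before the next dose. None is limited to particular visits.

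Sampling starts on the first day of treatment. For the sparse group, including switch patients, section 4.1 says that "sparse post-dose PK samples on Week 1 Day 1 and trough PK samples will be collected". Table 7-8 (sparse and switch patients) and Table 7-9 (full PK group) both open with a 2-hour sample on Week 1 Day 1, with a window of ± 10 minutes.

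For reporting, section 10.5.4 uses the PAS and says that summary statistics "will be presented for plasma concentration at each scheduled time point". The listing uses a different set: "Using Safety set, concentration data will be listed".

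Section 7.2.3 also contains a three-day requirement, but ties it only to the day of full PK profiling.

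**The concern.** A rule for steady-state samples has been written as a rule for all samples. One scheduled time point then has no evaluable concentration by definition, while the analysis section promises statistics for it. Two programmers working from this text could reasonably produce different tables: one with an empty Week 1 Day 1 row, the other with that row filled from values that the plan itself calls non-evaluable.

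PAS membership is also affected. A patient who stops before Week 2 and has only the first-dose sample has no evaluable concentration and is left out, although the sample was taken as scheduled. What is at stake is a descriptive output and the definition of an analysis set, not a test or an estimate of treatment effect.

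**Working it through.** The plan gives no figure to reproduce here. The check compares the dosing time available before each scheduled sample with the three days required.

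**Inputs**
- Required dosing before sampling: 3 days (section 10.1.5).
- Week 1 Day 1 sample: 2 h ± 10 min after the dose (Tables 7-8 and 7-9).
- No asciminib before that dose. Exclusion criterion 15 in section 5.3 bars "Previous treatment with or known/ suspected hypersensitivity to asciminib or any of its excipients", and switch patients come from bosutinib.
- Week 2 Day 1 visit window: ± 1 day (section 7.1.5).
- Planned asciminib allocation: 148 (section 10.8).

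**Time since first dose**
- Week 1 Day 1, latest in window: 2 h 10 min = 130 min; 130 / 1,440 = 0.09 day. This is below 3 days for every patient.
- Week 2 Day 1: nominally 7 days after first dose, so 7 − 1 = 6 to 7 + 1 = 8 days. This can meet the condition.
- Weeks 4, 12, 24 and 96: later still, so they can meet it if dosing was steady.

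**Samples per patient**
- Sparse schedule: 1 (Week 1) + 4 (Week 2) + 4 (Weeks 4, 12, 24, 96) = 9, of which 8 can be evaluable.
- Full PK schedule: 1 + 9 + 4 = 14, of which 13 can be evaluable.
- Week 1 Day 1 is the only scheduled sample that always fails.

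**Number affected**
- At the planned allocation: 148 × 1 = 148 if every patient is dosed and sampled.
- The rationale for Amendment 03-US.01 reports 233 patients randomised. If 2:1 held exactly, 233 × 2/3 ≈ 155 were on asciminib. The arm split is not given, so this is an assumption.
- Switch patients add one sample each only if they are summarised in the same way, which section 10.5.4 does not say.

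**Two readings of the PAS summary**
- *Non-evaluable concentrations are dropped.* The Week 1 Day 1 row has n = 0.
- *The PAS selects patients only.* First-dose values stay in for anyone with one later evaluable sample. So do later values taken after a dose interruption or after vomiting, and the per-sample conditions then do nothing beyond deciding who enters the set.
- Under both readings, a patient whose only sample is Week 1 Day 1 is outside the PAS.

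**Scope of the condition elsewhere**
Section 7.2.3 links the three days to the full PK day, which section 4.1 places on Week 2 Day 1. The Amendment 1 log explains the three-day figure in section 10.1.5 by the same full-PK-day requirement. Both suggest that the condition was meant for steady-state sampling.

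**After the correction below**, 9 of 9 sparse and 14 of 14 full-PK samples can be evaluable.

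**The case against.** The strongest defence is that the PAS is a set of patients, and that nothing in sections 10.1.5 or 10.5.4 says in so many words that a PAS patient's non-evaluable concentrations are removed from the summaries. That is correct, and it is why the empty row is the natural reading rather than a stated consequence. It does not rescue the text: the patient-level reading makes the per-sample conditions pointless for later visits, and the plan does not say which reading applies.

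Three stronger conclusions are tempting and should not be drawn.
- *A reader might infer that first-dose data are lost, or lost to the secondary PK objective.* They are not. All concentrations are listed on the Safety Set, and the optional population PK modelling (section 10.5.4) and ECG exposure-response work (section 10.6.2) are not tied to the PAS. The endpoints that Table 3-1 gives for this objective are trough concentrations and, in the full PK group, Cmax, Tmax, AUC0-12h and CL/F. A single 2-hour first-dose value feeds none of them.
- *A reader might infer that a planned comparison of first-dose with steady-state exposure is blocked.* No such comparison is specified in Table 3-1, section 10.5.4 or Table 10-1.
- *A reader might take 148 as a minimum.* It is the planned allocation; undosed patients or missed draws would reduce the count.

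Only the second of three parts of the combined document was available to me, so an exception elsewhere cannot be ruled out. None appears in the sections that define and use the PAS.

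**Conclusion.** The inconsistency stands. Under section 10.1.5 as written, the Week 1 Day 1 and S-Week 1 Day 1 concentrations can never be evaluable, and section 10.5.4 promises statistics for that time point on the set built from this rule. The effect is 1 of 9 or 1 of 14 scheduled samples per patient and is confined to one row of the descriptive PAS summaries and to PAS membership for patients with no later evaluable sample.

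That the row is empty rests on one assumption: that non-evaluable concentrations are left out of the PAS summaries. That the sample cannot be evaluable, and that a patient with only that sample is excluded from the PAS, does not depend on it. This is a wording correction that should be made before the PK tables are programmed; no main conclusion of the trial depends on it.

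**What to change.** Amend section 10.1.5, and the matching SAP text if it repeats the rule, in three respects:
- Apply the three-day same-dose condition only to samples from Week 2 / S-Week 2 onward, consistent with section 7.2.3.
- For Week 1 Day 1 and S-Week 1 Day 1, treat a concentration as evaluable if the first dose was taken before sampling and the existing 4-hour vomiting criterion is met.
- State that non-evaluable concentrations are excluded from the PAS summaries, while the Safety Set listing continues to show all of them.

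The cost is a few lines of text. Sampling, dosing and visit schedules do not change, and no other planned analysis is affected.
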